10.6 Safety Analysis

Cochlear implant safety results will be analyzed for each subject individually. The data will be described using conventional descriptive statistics. Data analyses will be conducted using appropriate non-parametric statistical tests. Safety outcomes from patients enrolled in the current study will be compared to data collected from patients with single sided deafness who do not undergo cochlear implantation using standard statistical tests. For all statistical

analyses, a p \leq 0.05 level of significance will be used. Any subsequent deviations from the statistical plan will be described and justified in a protocol amendment and/or in the final report submitted to this application.

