3. STUDY DESIGN

3.1 Study Design Description

The study of the MAESTRO Cochlear Implant system in patients with single sided deafness will be conducted as a prospective study with ten patients undergoing cochlear implantation (ten patients total). Pre-operative baseline measures will be obtained as outlined below. Post-operative evaluations will be conducted at initial device activation, and three, six, and twelve months post-activation. Because the presence or absence of a cochlear implant is easily recognized from visual inspection, blinding and masking procedures will not be utilized as part of the study design. The safety of the implant will be determined by monitoring major and minor complications in the cohort of study participants.

Candidates that are suitable for surgery will undergo placement of a cochlear implant. The cochlear implant wires will then be placed in the cochlea and tested intra-operatively. After confirmation of optimal electrode array placement, the receiver will be implanted within the temporal bone posterior to the pinna. The overlying subcutaneous tissue and skin will then be closed and covered with dressings using standard surgical techniques. Intra-operative imaging with a reverse Stenver X-ray will be performed to confirm proper electrode placement.

Following surgical implantation of the MAESTRO Cochlear Implant and two to three weeks of healing, the device will be activated and auditory performance will be assessed at the time of activation and at three, six, and twelve months post-activation. Subjects will be evaluated with the prior approved cochlear implant speech processor programmed with an approved sound-processing algorithm. Post-operative auditory function will be tested with a battery of pure tone threshold audiometry, word recognition testing, and spatial hearing testing. The degree of tinnitus present will be assessed using the Tinnitus Handicap Inventory.

The detailed list of assessments includes:

Prior to Surgery

Important baseline and control tests will be performed pre-operatively to obtain data for comparison. These will include:

 Modified Hearing Handicap Inventory and Quality of Life (SF-36) questionnaires will be administered (see attached)

- Tinnitus Handicap Index and Auditory Brainstem Response (ABR) testing
- Psychophysical measures

• Spatial hearing testing at the Binaural Hearing and Speech Lab at the University of Wisconsin - Madison ([name] lab)

Initial Activation

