5.2 Study Drug/Device Compliance/Adherence

Because the cochlear implant system is an implanted device, there are few concerns regarding compliance and adherence compared to most drug-based clinical trials. Our study is designed as a prospective, repeated-measure single subject trial. Participants in the experimental group will serve as their own controls. Throughout the study, we will confirm that subjects have been using the device through routine clinical follow-up and questionnaires at each appointment. Both qualitative and quantitative measures will be obtained to determine if subjects are benefiting from the cochlear implant system, and the individual activation parameters at each visit will be compared to the prior visit to ensure that settings on the device have not been altered or changed between visits.

Although we anticipate that the vast majority of subjects will derive a safe and substantial clinical benefit from use of the cochlear implant system, if a given subject is non-compliant or non-adherent with use of the cochlear implant system or external sound processor, then we will collect a final set of qualitative and quantitative measures and simply follow their outcomes through routine clinical exams. This approach will allow for monitoring of any

adverse safety or health concerns that may arise. Thus, no subjects in our study will be formally withdrawn for non-compliance or non-adherence and all study participants will be followed for one year after cochlear implant surgery. Any patient choosing to withdraw from the study will be replaced by a new study participant recruited from the clinic. The reasons for withdrawal or termination will of course be reported and documented at the time of occurrence.

If a subject withdraws or is terminated after implantation, a new subject will replace him or her. In principle, then, more than 10 subjects may end up with an implant based on their participation in the study.

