10.3 Sample Size Determination

Our study will recruit ten participants for placement of a MAESTRO Cochlear Implant device with follow-up measurements and assessments for one year post-operatively. Although our study is limited to a small sample size of ten patients, the single subject research design will allow each subject to serve as his or her own control, accommodating heterogeneity of the subjects' backgrounds and providing adequate power to test the major hypotheses. Previous studies have used a similar study design and sample size, with statistically significant findings regarding efficacy and safety of cochlear implants in patients with single sided deafness. Given that single-sided deafness is an experimental indication for cochlear implantation, it is appropriate to assess efficacy in a small cohort prior to recruiting more subjects. This will allow us to avoid unnecessary surgery in patients who may not benefit from this intervention.

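### Section 10.6 leads with subject-by-subject safety testing and never commits to a cohort complication proportion with an interval, so how little about ten subjects can exclude goes unstated

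*Combined protocol and SAP*

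**What the plan says.** Section 3.1 sets the safety question at the level of the group: "The safety of the implant will be determined by monitoring major and minor complications in the cohort of study participants".

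Section 10.6 starts from the individual: "Cochlear implant safety results will be analyzed for each subject individually". It continues: "The data will be described using conventional descriptive statistics". Then: "Data analyses will be conducted using appropriate non-parametric statistical tests". These sentences are nearly the same as those in Section 10.5 for effectiveness. Section 10.6 adds one group-level element, a comparison with an outside group: "Safety outcomes from patients enrolled in the current study will be compared to data collected from patients with single sided deafness" who are not implanted. The source and size of that group are not given. The significance level is 0.05.

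On numbers, Section 10.3 states: "Our study will recruit ten participants for placement of a MAESTRO Cochlear Implant device". It concedes in general terms that the sample is small, but calls the power adequate and points to earlier studies of similar size that reported significant safety results. Section 5.2 allows the implanted number to grow through replacement of withdrawals: "In principle, then, more than 10 subjects may end up with an implant based on their participation in the study". Section 10.4 keeps the data of withdrawn subjects in the safety analyses.

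**The concern.** There are two gaps between what Section 3.1 needs and what Section 10.6 commits to.

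- **Method.** Subject-by-subject analysis with non-parametric tests makes sense in Section 10.5, where the same ear is measured before and after implantation. A surgical or device complication has no pre-implant counterpart in that subject, so a within-subject test has nothing to compare.
- **Summary.** The result that would answer Section 3.1 is how many implanted subjects had a major or minor complication, and how precisely that is known. Section 10.6 does not name it.

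What is at stake is the reading of a good result. Section 10.3 calls single-sided deafness an experimental indication for implantation, and Section 10.1 expects to learn whether implantation improves safety compared with no treatment. If no complications occur and no interval is attached, a reader may take that as evidence of safety in this indication, although ten subjects can exclude only high complication rates.

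**Working it through.** **What can be reproduced.** Nothing. The ten participants in Section 10.3 come with no complication rate, effect size, standard deviation or numeric power. The check is therefore what ten subjects can show about a complication proportion.

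**Inputs.** n = 10 (Section 10.3); n may exceed 10 (Sections 5.2 and 9.3). The documents give no expected or acceptable complication rate, so every true rate below is an assumption.

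**Step 1: exact (Clopper-Pearson) 95% limits for x events in n subjects.**

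Lower limit = 2.5% quantile of Beta(x, n − x + 1), or 0 if x = 0. Upper limit = 97.5% quantile of Beta(x + 1, n − x). For x = 0 the upper limit reduces to 1 − 0.025^(1/n) two-sided, or 1 − 0.05^(1/n) one-sided.

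| Subjects with a complication | Observed | Exact two-sided 95% interval |
|---|---|---|
| 0 of 10 | 0% | 0 to 30.8% |
| 1 of 10 | 10% | 0.3 to 44.5% |
| 2 of 10 | 20% | 2.5 to 55.6% |
| 3 of 10 | 30% | 6.7 to 65.2% |

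For 0 of 10, the one-sided 95% upper limit is 1 − 0.05^(1/10) = 25.9%.

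**Step 2: chance that ten subjects show no case at all, (1 − p)^10.**

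| Assumed true rate p | Calculation | Chance of no case |
|---|---|---|
| 5% | 0.95^10 | 59.9% |
| 10% | 0.90^10 | 34.9% |
| 20% | 0.80^10 | 10.7% |

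For a 95% chance of at least one case, the true rate must be 1 − 0.05^(1/10) = 25.9%.

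**Step 3: effect of replacement on the denominator.** With no events, the two-sided upper limit is 1 − 0.025^(1/11) = 28.5% for 11 implanted and 1 − 0.025^(1/12) = 26.5% for 12. A few replacements barely change the precision. The denominator still needs stating, because Section 10.4 refers to ten patients and to all participants without saying whether a proportion would be taken over those enrolled, implanted or completing.

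**Step 4: the sections side by side.** Section 3.1 needs a cohort result. Section 10.6 gives the individual as unit, leaves the descriptive statistics and tests unnamed, and adds an external comparison. Section 8.1 says only that safety outcomes will be analysed after completion. None of them supplies a proportion, a denominator or an interval.

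**The case against.** The strongest reply is that a cohort summary is already implied. For complications, ordinary descriptive statistics are counts and percentages, and comparing enrolled patients with a non-implanted group requires a group figure. This stands. A reader might infer from the opening sentence of Section 10.6 that no complication rate would be produced at all; the rest of the section does not support that. The summary is unspecified, not excluded.

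A reader might also infer that subjects who withdraw and are replaced would drop out of the safety result. Section 10.4 says the opposite, and Section 13.1 continues collection to one year after surgery in withdrawn subjects who agree. What remains open is only the denominator.

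Nor is a subject-level account empty. Safety is assessed at activation and at each later visit (Section 3.1), and each adverse event is assessed for seriousness and causality (Section 9.1). With about ten subjects, a listing is useful. The objection to the individual approach applies to significance tests on complications, not to description.

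Finally, the verb in Section 3.1 could be read as a claim of statistical precision. It need not be: that section names no proportion or threshold, and safety is not among the five hypotheses at the end of Section 1.2. Section 11.1 adds that the device's risks are known from bilateral use. These points reduce the weight of the concern. They do not supply the missing summary, and Section 10.3 itself treats the indication as experimental and cites safety findings in support of this sample size.

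**Conclusion.** The concern holds in a limited form. Section 10.6 leads with a method that does not suit complications, and no section commits to a cohort complication proportion or its uncertainty, although Section 3.1 judges safety in the cohort. The general remarks about a small sample do not say what this means for safety.

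The size is clear: 0 of 10 leaves true rates up to 30.8% compatible with the data (two-sided 95%; 25.9% one-sided). A complication with an assumed true rate of 10% would go entirely unseen in about 35% of such cohorts. The intervals depend only on the number of subjects and on treating subjects as independent. The 5%, 10% and 20% rates are illustrations, since the documents give none.

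This is a change worth making in how safety is summarised and read. It does not mean that safety data would go uncollected or that a safety claim has been made.

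**What to change.** In Section 10.6:

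- Make the main safety summary the number and proportion of implanted subjects with at least one major complication and, separately, with at least one minor complication, each with an exact 95% confidence interval.
- Define the denominator as every implanted subject, including those who later withdraw or are replaced. It may exceed ten, and this agrees with Section 10.4.
- Keep a listing of events by subject as a supplement.
- Drop within-subject significance tests for complications.
- State in advance that 0 of 10 would still be compatible with a true rate up to 30.8% (two-sided 95%; 25.9% one-sided), and recompute the limit if more than ten are implanted.

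A softer verb in Section 3.1 is optional. The cost is a few sentences and one small table, with no new data and no change to how subjects are managed. The downside is a less favourable safety statement.

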9. ADVERSE EVENT RECORDING AND REPORTING

9.1 Recording Requirements

Research subjects will be routinely questioned about adverse events at study follow-up visits.

> RECORDING REQUIREMENT

All observed or volunteered adverse events (serious or non-serious) and abnormal test findings, regardless of suspected causal relationship to the study device will be recorded in the subjects' case histories (source data, case report form). For all adverse events, sufficient information will be obtained to permit 1) an adequate determination of the outcome of the event (i.e., whether the event should be classified as a serious adverse event) and; 2) an assessment of the casual relationship between the adverse event and the cochlear implant system.

Adverse events or abnormal test findings felt to be associated with the cochlear implant system will be followed until the event (or its sequel) or the abnormal test finding resolves or stabilizes at a level acceptable to the Sponsor-Investigator.

> ABNORMAL TEST FINDINGS

An abnormal test finding will be classified as an adverse event if one or more of the following criteria are met:

- The test finding is accompanied by clinical symptoms
- The test finding necessitates additional diagnostic evaluation(s) or medical/surgical intervention, including significant additional concomitant drug treatment or other therapy
- The test finding leads to discontinuation of subject participation in the clinical research study
- The test finding is considered an adverse event by the Sponsor-Investigator of the IND or IDE application

> CASUALTY AND SEVERITY ASSESMENT

The Sponsor-Investigator of the IND or IDE application will promptly review documented adverse events and abnormal test findings to determine 1) if the abnormal test finding should be classified as an adverse event; 2) if there is a reasonable possibility that the adverse event was caused by the MAESTRO cochlear implant system; and 3) if the adverse event meets the criteria for a serious adverse event.

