10.4 Analysis Population

Given the small sample size of ten patients for our study, we will plan to analyze data obtained from all participants. If a subject withdraws from the study, data obtained from their participation in the study will still be incorporated into outcomes and safety analyses.

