13. STUDY DISCONTINUATION CRITERIA

13.1 Discontinuation of Individual Research Subjects

As described, safety measures will include complications questionnaires and frequent postoperative follow-up visits. Inquiries about both major and minor complications will be made and any complications will be recorded. A research assistant will regularly review safety measures every month for all study participants and discuss any safety concerns/adverse outcomes with the investigator. The investigator will then decide whether the research study should be altered or stopped. If a clear answer is not evident, the investigator will discuss the safety concern with the Human Studies Committee and make appropriate adjustments to the study as needed. Other discontinuation criteria are described under Section 5.2 (Withdrawal of subjects due to non-compliance/adherence) and section 9.3 (Withdrawal of subjects due to adverse events) of the clinical protocol.

If withdrawn subjects agree to measurements of clinical outcomes and assessments of device safety, their data will be collected until one year following cochlear implantation surgery. As with other criteria for withdrawal, subjects that are withdrawn will be replaced through recruitment of additional study participants in clinic.

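### Section 10.6 tests safety against an undescribed non-implanted group; for complications of surgery or device the test is uninformative, and once anyone is affected its verdict depends on that group's size

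*Combined protocol and SAP*

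**What the plan says.** Section 10.6 opens with "Cochlear implant safety results will be analyzed for each subject individually", promises descriptive statistics, and adds "Data analyses will be conducted using appropriate non-parametric statistical tests". It then commits to a group comparison: safety outcomes will be "compared to data collected from patients with single sided deafness who do not undergo cochlear implantation using standard statistical tests". The p<=0.05 level covers all analyses in that section. Neither the test nor the safety outcome to be tested is named.

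The comparator is not an arm of this study. Section 3.2 has no allocation, and section 5.2 makes subjects their own controls. Sections 10.1 and 10.2 mention data from non-implanted patients again without describing them. Section 10.1 expects such comparisons to show whether implantation is safer, as well as more effective, than no treatment.

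On what counts as safety, section 3.1 says: "The safety of the implant will be determined by monitoring major and minor complications in the cohort of study participants". Section 9.1 records more widely: "All observed or volunteered adverse events (serious or non-serious) and abnormal test findings, regardless of suspected causal relationship to the study device".

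On who is counted, section 5.2 allows that "more than 10 subjects may end up with an implant based on their participation in the study", because withdrawn subjects are replaced. Section 10.4 says of withdrawn subjects that "data obtained from their participation in the study will still be incorporated into outcomes and safety analyses". Section 13.1 says that, if they agree, "their data will be collected until one year following cochlear implantation surgery".

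**The concern.** A complication of surgery or of the device needs an operation or a device. In a group with neither, the rate is zero by construction, so equality of rates is known to be false as soon as the true rate in implanted patients is above zero. A significant result then says only that surgical complications follow surgery, and a non-significant one reflects how few people were compared. Describing the comparator better would not cure this.

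What is at stake is how the final safety result is read. With a small comparator, a non-significant p-value could pass for reassurance, especially given what section 10.1 expects. With a larger one, the same count becomes a significant finding. Nothing in section 10.6 promises a statement of how high the complication rate could still be, which is the question that a cohort of ten can inform.

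**Working it through.** **Inputs.** Ten implanted subjects (section 10.3) and p<=0.05 (section 10.6). The comparator size m, the true complication rates and the background rate are assumptions, because the documents give none. Section 10.3 states ten subjects without an event rate, effect size or power figure, so there is no calculation of the plan's own to reproduce.

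**1. Complications that cannot occur in the comparator.** Compare k/10 with 0/m by Fisher's exact test. The probability of the observed table is

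C(10,k) / C(10+m,k).

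For m of 11 or more this is also the two-sided p-value, because the opposite extreme is more probable than the observed table. At m=10 the opposite tail doubles it; at smaller m, any opposite-tail tables no more probable than the observed one are added.

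- k=1: 10/(10+m) <= 0.05 needs m=190 (10/200 = 0.0500).
- k=2: m=33 gives 90/(43×42) = 0.0498; m=32 gives 0.0523.
- k=3: m=10 gives 2×720/(20×19×18) = 0.21; m=15 gives 0.0522; m=16 gives 720/(26×25×24) = 0.0462; m=20 gives 720/(30×29×28) = 0.030.
- k=4: m=10 gives 0.0867; m=11 gives 5040/(21×20×19×18) = 0.0351.
- k=5: m=6 gives 0.0934; m=7 gives (252+21)/6188 = 0.0441.
- k=6: the threshold is m=5 (p=0.044).
- k=0: p=1 at any m.

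**2. Sensitivity to the unnamed test.** Smallest m giving p<=0.05:

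| Affected of 10 | Fisher two-sided | Fisher one-sided | Chi-square uncorrected | Chi-square corrected |
|---|---|---|---|---|
| 1 | 190 | 190 | 38 | 173 |
| 2 | 33 | 33 | 18 | 40 |
| 3 | 16 | 16 | 11 | 21 |
| 4 | 11 | 10 | 8 | 14 |
| 5 | 7 | 7 | 6 | 10 |

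The thresholds move with the test. The dependence on m does not go away.

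**3. How likely the affected counts are.** P(1 to 4 affected) is the sum over j = 1 to 4 of C(10,j) π^j (1−π)^(10−j). For π = 5%, 10%, 20% and 30% this is 40%, 65%, 86% and 82%. At 5%, the chance of 0/10 is 0.95^10 = 60%.

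**4. Chance of p<=0.05 by comparator size.** Two-sided Fisher needs at least 5, 3, 2 and 1 affected for m = 10, 20, 50 and 200. At π = 20% the chances are 3%, 32%, 62% and 89%. At π = 10% they are 0.2%, 7%, 26% and 65%.

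**5. Events with a background rate, assumed 10% in the comparator.** 3/10 gives p=0.12 against 5/50, 0.095 against 10/100 and 0.073 against 100/1000, so it stays non-significant. 4/10 gives p=0.30 against 1/10 and 0.034 against 5/50. The result depends on the comparator's rate as well as its size.

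**6. What the cohort alone can say.** Exact (Clopper-Pearson) 95% intervals: 0/10, 0 to 30.8% (upper limit 1 − 0.025^(1/10)); 1/10, 0.3 to 44.5%; 2/10, 2.5 to 55.6%; 3/10, 6.7 to 65.2%; 4/10, 12.2 to 73.8%. With zero events the upper limit is 28.5% if 11 are implanted and 26.5% if 12. No comparator is needed.

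**The case against.** The plan already promises descriptive statistics, so the counts will be reported and anyone can compute an interval from them. Ten subjects is a deliberately small first cohort, and the comparator could still be specified. Adverse events are recorded whatever their cause, so for events that also occur without an implant a comparison is not empty. At a true complication rate of 5%, the likeliest single result is 0/10, where comparator size is irrelevant.

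Most of this stands as a limit on the point. It does not rescue the test for complications of surgery or the device, because no specification of the comparator makes those possible in people without either. For events with a background rate, a comparison can carry some information, but it is open to confounding without common ascertainment.

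A reader might go further in three ways that the documents do not support.

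- That every significance test of safety should go. Subjects are their own controls and abnormal test findings are recorded, so the sentence on non-parametric tests can cover before/after comparisons that need no outside group.
- That a stopping or reporting decision would turn on this p-value. No explicit rule uses it, and section 13.2 states no known criteria for discontinuing the study. The interim analyses in section 10.7 do not specify their content, so their use of this comparison is neither planned nor excluded.
- That comparator size matters only for 1 to 4 affected. The verdict still flips at 5/10 (7 comparators) and 6/10 (5 comparators); those sizes are simply very small.

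**Conclusion.** The point holds for complications caused by surgery or the device. For these the planned test is uninformative, and with at least one subject affected its verdict is set in part by a comparator size that the plan does not state. At an assumed true rate of 20%, the chance of significance runs from 3% with 10 comparators to 89% with 200.

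The figures rest on assumed sizes and rates, a comparator count of zero and two-sided Fisher; the exact thresholds would change with another test, the conclusion would not. Replacement may bring the implanted number above ten, which shifts the thresholds only. For events possible in both groups the conclusion is weaker: the comparison is underspecified and open to confounding, not empty. Either way, it cannot support the statement in section 10.1 about better safety than no treatment.

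This should be changed, because a better summary is available at almost no cost. The consequence is confined to interpretation as far as the documents show.

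**What to change.** In section 10.6, delete the significance test against non-implanted patients, so that p<=0.05 no longer applies to that comparison. Add:

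*The number and proportion of all implanted subjects, including those withdrawn and their replacements, with at least one major and with at least one minor complication will be reported, each with an exact (Clopper-Pearson) 95% CI based on the actual number implanted. Length of follow-up will be shown for subjects who withdraw.*

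Note beside it that 0/10 leaves an upper limit of 30.8%. Keep individual results as listings, and word the sentence on individual analysis so that it agrees with the group proportions. Use outside data on non-implanted patients only as descriptive context for events that can occur in both groups, with source, size, follow-up and ascertainment stated. Within-subject before/after tests of safety measures may stay.

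In section 10.1, strike the words *safety and* from the closing statement about improvement over no treatment. This point requires no change to the efficacy and tinnitus comparisons in sections 10.1 and 10.2.

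The cost is wording only: no new data, visits or subjects. The between-group safety p-value is lost, and the intervals will be wide.
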